**5.4.26 Debriefing**

Not applicable.

**5.5 Informed consent will not be obtained – request to completely waive the informed consent requirement**

**5.5.21 Indicate why the research could not practicably be carried out without the waiver of consent**

Not applicable.

**5.5.22 Describe why the research involves no more than minimal risk to subjects.**

Not applicable.

**5.5.23 Describe why the alteration/omission will not adversely affect the rights and welfare of subjects.**

Not applicable.

**5.5.24 If the research involves using identifiable private information or identifiable biospecimens, describe why the research could not be practicably be carried out without using such information or biospecimens in an identifiable format.**

Not applicable.

**5.5.25 Additional pertinent information after participation**

Not applicable.

**5.6 Consent – Other Considerations**

**5.6.21 Non-English-Speaking Subjects**

Not applicable.

**5.6.22 Cognitively Impaired Adults**

**5.6.2.1 Capability of Providing Consent**

Not applicable.

**5.6.2.2 Adults Unable to Consent**

Not applicable.

**5.6.2.3 Assent of Adults Unable to Consent**

Not applicable.

**5.6.23 Subjects who are not yet adults (infants, children, teenagers)**

**5.6.3.1 Parental Permission**

Not applicable.

### 5.6.3.2 Assent of subjects who are not yet adults

Not applicable.

## 6.0 HIPAA Research Authorization and/or Waiver or Alteration of Authorization

### 6.1 Authorization and/or Waiver or Alteration of Authorization for the Uses and Disclosures of PHI

Check all that apply:

- Not applicable, no identifiable protected health information (PHI) is accessed, used or disclosed in this study.** *[Mark all parts of sections 6.2 and 6.3 as not applicable]*
- Authorization will be obtained and documented as part of the consent process.** *[If this is the only box checked, mark sections 6.2 and 6.3 as not applicable]*
- Partial waiver is requested for recruitment purposes only (Check this box if patients' medical records will be accessed to determine eligibility before consent/authorization has been obtained).** *[Complete all parts of sections 6.2 and 6.3]*
- Full waiver is requested for entire research study (e.g., medical record review studies).** *[Complete all parts of sections 6.2 and 6.3]*
- Alteration is requested to waive requirement for written documentation of authorization (verbal authorization will be obtained).** *[Complete all parts of sections 6.2 and 6.3]*

### 6.2 Waiver or Alteration of Authorization for the Uses and Disclosures of PHI

#### 6.2.1 Access, use or disclosure of PHI representing no more than a minimal risk to the privacy of the individual

Not applicable.

#### 6.2.2 Explanation for why the research could not practicably be conducted without access to and use of PHI

Not applicable.

#### 6.2.3 Explanation for why the research could not practicably be conducted without the waiver or alteration of authorization

Not applicable.

### 6.3 Waiver or alteration of authorization statements of agreement

Not applicable.

## 7.0 Study Design and Procedures

## 7.1 Study Design

This study will use a convergent mixed methods design to: 1) explore how playing the serious game, “Who Would You Choose” (WWYC), affects individuals’ choice of a spokesperson; 2) establish the feasibility of using WWYC for helping people designate an appropriate spokesperson for healthcare decisions and 3) receive a positive response from the spokesperson which will be confirmed with a completed REDCap survey. In each game event (lasting ~2 hours), research staff will help facilitate game-play for groups of 4 players, who will also 1) complete baseline questionnaires, 2) complete post-game questionnaires, and 3) participate in post-game focus group discussions. Then, players will use text messages initiated by the associated WWYC smartphone App to engage their chosen spokespersons by sending a text message inviting them to complete a brief REDCap survey asking what medical preferences they think the player would want in various clinical scenarios. If this spokesperson does not respond or complete the survey within one week, the player may forward the same test message with REDCap survey link to an alternate spokesperson. If the alternate spokesperson does not respond or complete the survey, no additional spokespersons will be contacted. Approximately 2 weeks after the game event, players will be contacted by phone for a one-on-one interview.

Game piece examples:

## 7.2 Study Procedures

Prior to Game Play:

- After eliciting informed consent, participants will be asked to complete the following :

- Demographics (i.e. age, race/ethnicity, religiosity, education, gender, experience with surrogate medical decision-making, experience playing games, attitudes about ACP)
- Stage of Readiness to engage in ACP
- Choosing a Spokesperson (pre-activity)
- Install WYWC game app onto their personal smart phone

#### Game Play:

WWYC is played with 4 - 6 individuals via a smart phone app with card game components. Players 1) enter answers to game questions, 2) guess which player entered each answer (with points awarded for correct guesses), and 3) explain why they answered the way they did. The other players then decide whether a given player's explanation is good (merits an extra point), OK (no extra point), or poor (merits taking away a point). In addition to the "game choice," players also enter a "real-life choice" for each question –which is not shared, but will help them with the game's final question.

Across the 7 rounds, the game questions are intentionally unrelated to medical care so as to create a playful environment that still encourages players to reflect on spokesperson qualities. Game-play concludes after 7 rounds are completed (<1 hour), and a "winner" is identified by having the highest number of points earned. Then, one player reads instructions allowed to direct each player to choose a spokesperson (see Box 2).

There are 7 rounds to the game, corresponding to 7 qualities that a good spokesperson (or surrogate medical decision maker) should possess. These qualities were identified from a review of the literature and our pilot work (see Preliminary Data). For each round/quality, there are 11 question cards, and a roll of the dice determines which question is to be answered for that round. The player who rolled the dice also flicks a spinner to narrow

Box 2. Now that you have played "Who Would You Choose," there is one final question to answer. This question is just for you, and you don't need to share your answer with the other players. Please reflect on the choices you made, and what this says about your priorities and values when it comes to making medical decisions. Now, imagine being in a situation where you were unable to make medical decisions for yourself, and someone else needed to make them for you. What kind of person would you want to take on that role as your surrogate decision-maker (also known as a spokesperson)? To start, it should be someone who knows you well. But experts agree that this person should have other characteristics as well –specifically, those described on the question cards. So, ideally, this person would be available when needed, and would be someone you trust, is caring, would honor your wishes, can stand up under pressure, has good judgment, and shares your values. Please review the list of characteristics and your responses. When you are ready, write down the name of the person in your life who best embodies these qualities and who you would want to make medical decisions for you should the need arise. This individual is called your "surrogate decision-maker" and acts as your spokesperson.

game-choices to 1 of 4 general categories (Public figure, Fictional character, Entertainer, or Historical figure). After the question is read aloud each player enters a game-choice (which gets shared), as well as a "real-life choice" (which does not get shared). If players need help coming up with a game-choice, they may choose from the "Need-a-Name" options. In this version of WWYC, both answers and guesses will be recorded using a smart-phone App, but in our test version (see Preliminary Data) players wrote responses manually.

The WWYC smart-phone App will supplement the cards, dice, and spinner to provide a secure dynamic database for up to 6 players at a time. Once the game question for a given round has been selected, and each player has typed a response using their smart-phone, the App will display all responses, and allow players to guess which player gave which response. The App will keep track of players' scores (reflecting the number of correct guesses), as well as point totals. Because the App is also intended to promote engagement with spokespersons, the App will allow players to invite their spokesperson to participate. Through the App, participants will share a link with their spokesperson via text message.

Research staff coordinating the game event will visually confirm participants have forwarded this survey to their potential spokesperson. By clicking the link, the spokesperson will view the Summary Explanation of Research, confirm willingness to participate, and provide basic demographic information through REDCap. Should this spokesperson not respond after seven days, the player may forward the survey invitation link to an alternative spokesperson. Should the alternate not respond, no additional invitations will be sent. Upon leaving the event, participants will be given a formal healthcare power of attorney form to complete. Additionally, ~2 weeks after the event, the research team will contact participants by phone to conduct follow-up interviews.

Post-Game Outcomes Measured:

- Experience/process of game-play (i.e., one-on-one interviews, focus groups)
- Net Promoter Score
- Stage of Readiness to Choose a Spokesperson
- Choosing a Spokesperson
- Spokespersons' Engagement with Online Interface
- Player Evaluation

## 7.2 Duration of Participation

Players:

- Up to 2 hours. Anticipated time allotment is as follows:
- 5-10 minutes Informed Consent
- 5-10 minutes Explanation of game
- 45-60 minutes Game
- 30-40 minutes Feedback from participants
- 20-30 minute follow-up phone interview

Spokespersons (Surrogates):

- 15-20 minutes to read and complete online survey

## 8 Subject Numbers and Statistical Plan

### 8.2 Number of Subjects

Up to 800 participants (400 players and 400 spokespersons, with each game consisting of 4 players each)

### 8.3 Sample size determination

Using purposive sampling, aim to recruit 50% female and >25% ethnic/racial minority participants. As a feasibility study, the main objective is to establish viability of the intervention rather than efficacy. Thus a power analysis is not necessary. The sample size reflects the number of participants we expect to be able to recruit in this time period to obtain the information necessary to answer study questions.

### 8.4 Statistical methods

**Quantitative data** will be analyzed by first summarizing all variables with frequencies and percentages, or means, standard deviations, medians, and quartiles. The primary outcome variables will then be defined based on criteria stated above and summarized with frequencies and percentages to determine

if they reach the needed feasibility levels. As a feasibility study, we are not performing statistical testing or seeking significance as a primary goal. All analyses will be performed using SAS version 9.4

**Qualitative data** will undergo conventional content analysis to identify emergent themes—with focus groups and 1:1 interviews analyzed separately. All inter-disciplinary team members will review 20% of transcripts independently to create broad categories. Categories and subcategories will then be organized into a preliminary codebook, and exemplars selected to further define the codes—which will then be used to code an additional 20% of transcripts using the constant comparison method.

**Biological variables** including age and gender will be assigned as attributes to examine effects on participant experiences. Inter-rater reliability will be judged using a kappa  $>0.7$ ; discrepancies will be managed by group discussion to arrive at consensus codebook for coding the entire dataset (2 coders per transcript). Experienced qualitative researchers ([name], [name]) will oversee analyses; coders will be trained by experienced members of the Penn State Qualitative Mixed Methods Core. Published criteria for **methodological rigor of qualitative research** will be used to attend to the truth-value, applicability, consistency, and neutrality of findings. To evaluate credibility (i.e., truth-value) of findings, a sub-set of participants will be asked to review a summary of data to ensure accuracy (member checking). To bolster applicability of findings to other contexts, rich/thick descriptions from interviews will be obtained to assess and compare experiences. Consistency and dependability of data will be maintained by inter-rater reliability analyses using intra-class correlation coefficients. Researchers will bracket biases and create an audit trail of coding decisions to maximize data neutrality.

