To address these gaps, we have developed a novel intervention that includes a “serious game” to help people consider the qualities they want in their spokesperson, then engage the person they choose for this role. Combining a serious topic with an enjoyable activity (“gamification”) has been effective at changing health related behaviors in multiple settings with our target population (“sandwich generation” and older adults). The game element of our intervention, “*Who Would You Choose: Serious Fun*” (**WWYC**), prompts players (using scenarios and metaphors) to choose a spokesperson whose qualities are best suited to the role. At the end of the game, players identify a real-life spokesperson based on the qualities considered during gameplay. Then, using an online interface, WWYC will spark communication between the player and their chosen spokesperson. The long-term goal of this project is to help people make more thoughtful and informed choices when selecting a spokesperson, and to help these spokespersons be better prepared for their role as surrogate decision-makers. The current mixed methods study proposed here is designed to learn whether and how WWYC helps individuals select an appropriate spokesperson for healthcare decisions, as assessed via three **Specific Aims**:

**Aim 1 (QUALITATIVE):** To explore how playing a novel game affects people's choice of a spokesperson. Qualitative focus groups will be used to examine the group experience playing WWYC. One-on-one interviews will be used to explore how the game affected individual players' thought process for choosing a spokesperson, and whether that choice changed as a result of game-play.

**Aim 2 (QUANTITATIVE):** To establish that WWYC is a feasible way to help individuals choose and engage a spokesperson. We will judge WWYC as feasible if:

- We can efficiently recruit 100 individuals to play the game;
- $\geq 75\%$  of game players report that playing the game is helpful for choosing a spokesperson;
- $\geq 75\%$  of game players endorse the game, as measured by the Net Promoter Score;
- $\geq 75\%$  of spokespersons engage with WWYC (using its online interface) following player request

**Aim 3 (CONVERGENT MIXED METHODS):** To integrate qualitative and quantitative data via a joint display to explain how the experience of playing WWYC relates to their spokesperson's willingness to

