engage. We hypothesize that positive player experience with WWYC will be associated with successful engagement with their spokesperson.

If successful, this study will establish the feasibility of a serious game for helping people choose a spokesperson for medical decision-making, and result in the creation a fully functional prototype (including its online interface). We will then be positioned to conduct a randomized controlled trial evaluating the efficacy of WWYC (compared to standard methods) for improving concordance between patients' wishes and spokespersons' decisions on their behalf.

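### Does the 75% spokesperson-engagement criterion need a fixed numerator, denominator and time window in section 8.4?

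*Combined protocol and SAP*

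**What the plan says.** Aim 2 in section 1.1 is "To establish that WWYC is a feasible way to help individuals choose and engage a spokesperson". One of its four conditions is that at least 75% "of spokespersons engage with WWYC (using its online interface) following player request". Aim 3 adds the hypothesis that "positive player experience with WWYC will be associated with successful engagement with their spokesperson".

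Section 7.1 lists among the purposes of the design to "receive a positive response from the spokesperson which will be confirmed with a completed REDCap survey". It then allows one replacement when a week has passed without a reply or a finished survey: "the player may forward the same test message with REDCap survey link to an alternate spokesperson". The Game Play part of section 7.2 repeats the rule with a slightly different trigger: "Should this spokesperson not respond after seven days, the player may forward the survey invitation link to an alternative spokesperson". Both sections stop at one alternate. Section 7.2 also has staff check at the event that each player has sent the first request.

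Section 8.2 plans for up to 400 players and 400 spokespersons. Section 8.4 says that "The primary outcome variables will then be defined based on criteria stated above and summarized with frequencies and percentages", so that they can be set against the feasibility levels, and it states that testing is not a primary goal.

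**The concern.** Section 8.4 sends the reader back to the Aim 2 criterion, and that criterion does not settle how the percentage is formed once an alternate may be asked. Three readings can be argued:

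- **A:** players whose first-chosen spokesperson engaged, divided by players who sent a request.
- **B:** players for whom the first choice or the alternate engaged, divided by the same players.
- **C:** all spokespersons who engaged, divided by all who were asked.

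The literal wording of Aim 2 leans towards C, while section 8.2 and the Aim 3 hypothesis lean towards one outcome per player. No closing date is given, and nothing says how a late reply from the first choice counts once an alternate has been approached. The two triggers also differ: section 7.1 mentions responding or completing, section 7.2 only responding.

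At stake is the verdict on one of the four Aim 2 conditions, because the decision is a bare percentage against 75%. An optional second request can raise B although the game did no better at getting the first-chosen person to engage.

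**Working it through.** The plan has no derived figure to reproduce: 75% is a chosen threshold, and section 8.3 gives no power analysis. The check is therefore how far the readings can differ, and how many of them the text leaves open.

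**Counts.** The 100 players come from Aim 2; the other counts are assumptions. Let N = 100 players, a = 65 first choices complete, m = 20 alternates asked, b = 10 alternates complete.

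- A = a/N = 65/100 = 65%
- B = (a + b)/N = 75/100 = 75%
- C = (a + b)/(N + m) = 75/120 = 62.5%

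Scaled to the 400 players of section 8.2, these are 260/400, 300/400 and 300/480, the same percentages. Given a = 65, only m = 20 with b = 10 yields this exact trio, so the example is tuned to the threshold.

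**General case.** Let p1 be the first-choice completion rate, f the share of non-responses followed by an alternate, and r the alternates' completion rate relative to p1. All three are assumptions. Then A = p1, B = p1 + (1 − p1)·f·r·p1, and C = B/(1 + (1 − p1)·f). A reaches 75% at p1 = 75%. The other two reach it at:

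| f | r | B = 75% at p1 | C = 75% at p1 |
|---|---|---|---|
| 0.25 | 0.5 | 72.5% | 77.1% |
| 0.5 | 0.5 | 69.7% | 78.8% |
| 0.5 | 1 | 63.4% | 75.0% |
| 1 | 0.5 | 63.4% | 81.4% |
| 1 | 1 | 50.0% | 75.0% |

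If f = 0, A, B and C coincide. With light forwarding (first row), A and B disagree only for p1 between 72.5% and 75%. The widest disagreement needs every non-response to be followed up and alternates to complete as often as first choices.

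At p1 = 65%:

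- f = r = 0.5: B = 0.65 + 0.35 × 0.5 × 0.325 = 70.7%, which is 5.7 points above A.
- f = 0.5, r = 1: B = 0.65 + 0.35 × 0.5 × 0.65 = 76.4%, 11.4 points above A.
- f = r = 1: B = 0.65 + 0.35 × 0.65 = 87.75%, about 22.8 points above A.

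**What the text already settles.**

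1. *Event.* Section 7.1 says a positive response is confirmed by a completed REDCap survey, which fits the online interface named in Aim 2. The wording about not responding in section 7.2 is the trigger for approaching an alternate; it does not define engagement.
2. *Unit.* Aim 2 speaks of engaging a spokesperson, Aim 3 of the player's own spokesperson, and section 8.2 plans equal numbers of each. C fits these poorly.
3. *Late replies.* Under B a player counts once whichever person completes, so a late first-choice reply alongside an alternate's reply alters nothing. It matters only under A, and only if A carries a deadline. The seven days in sections 7.1 and 7.2 open the alternate route; neither section makes them an outcome cut-off.

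What remains open is A against B, and when counting closes.

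**The case for a change.** The strongest case for a change is that, with no test planned, the definition of the percentage is the whole analysis. Leaving it until the data are in lets the verdict be chosen. Treating players as independent, at a true first-choice rate of 65% reading A passes about 2% of the time with 100 players. Reading B passes about 20%, 68% or over 99% in the three settings worked above. For scale, the 95% interval half-width at 75% is 8.4 points with 100 players and 4.2 with 400, so the gap between readings can exceed sampling error. Writing down a definition would cost one paragraph.

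Much of this stands. No section says whether an alternate counts, and the direction of the effect is certain: B can never be below A. But the pass probabilities rest on forwarding and completion rates that the documents do not give, and on independence although play is in groups of four.

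The natural remedy, A with a seven-day limit, is not clearly better. It would class a first choice who completes on day eight as not engaged, and it would never credit an alternate whom the protocol expressly permits. A suits someone who sees the first-chosen person as the product of the game. B suits someone who asks whether a player ended up with an engaged spokesperson. Fixing B would close the gap equally well, which shows that the dispute is about preference and not about a faulty method.

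Whether first-choice and alternate replies can be told apart in the data cannot be judged here. The REDCap instruments are not in the documents, and section 22 defers data handling to a separate form.

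**Conclusion.** No change follows. This is an unwritten detail that analysts can fill sensibly. The event is largely given (a completed REDCap survey), the unit is most naturally the player, and the remaining choice between first choice only and either person is a fair trade-off. No rule in the plan is shown to give a wrong result, and either count is a valid descriptive percentage whose meaning is plain once its numerator and denominator are shown.

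The possible effect is nil if no alternate is asked. At a first-choice rate of 65% it is 5.7 to 22.8 points between A and B over the settings shown, all of them assumed. It touches one of four Aim 2 conditions in a descriptive feasibility study; Aim 3 uses engagement in a joint display and applies no 75% threshold. The conclusion rests on reading section 7.1 as the intended event and on sections 1.1 and 8.2 as implying one outcome per player. It would be weaker if the team meant every invited spokesperson to be the denominator, since the number of alternates asked would then enter the percentage.
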